17.2. Risks Associated with the Study Device

Overall, there are no incremental risks expected with the investigational device compared to similar mechanical circulatory support system devices on the market.

17.3. Risks Associated with Participation in the Clinical Study

Risks associated with HR-PCI and participation in this clinical study are listed above in **Table 17.1-1**.

17.4. Possible Interactions with Concomitant Medical Treatments

Medications to be used in the Vortex Feasibility Study constitute standard of care for subjects undergoing HR-PCI as described in society guidelines³.

17.5. Risk Minimization Actions

Additional risks may exist. Risks can be minimized through compliance with this protocol, performing procedures in the appropriate hospital environment, adherence to subject selection criteria, close monitoring of the subject's physiologic status during research procedures and/or follow-ups and by promptly supplying BSC with all pertinent information required by this protocol.

The aforementioned risks are mitigated with the following approaches.

- Estimation of risks associated with the investigational device in accordance with ISO 14971 prior to conducting the clinical investigation
- Preclinical testing and bench testing of the Vortex System to establish safety and performance
- Selection of investigators who are experienced and skilled in interventional HR-PCI procedures supported by mechanical circulatory support devices
- Completion of training provided by the sponsor
- Clearly defining the inclusion/exclusion criteria to ensure only appropriate subjects are enrolled
- Confirmation of eligible subjects by investigators experienced in HR-PCI with MCS procedures
- Performing all procedures in accordance with the Vortex System IFU
- Ensuring that treatment of subjects is consistent with current medical practices, including adjunctive pharmacologic therapy
- On-site support by BSC representatives during the procedure
- Dynamic safety review processes, with Independent Medical Reviewer (IMR) adjudication

Anticoagulation medication (e.g., heparin) will be administered during the procedure per standard of care to reduce the risk of thrombosis, embolism, and stroke.

Cardiac enzyme, serum creatinine and plasma free hemoglobin measurements and electrocardiograms will be performed post-procedure to detect cardiac or renal injury.

Subjects will be carefully monitored during the procedure, and through 72 hours or hospital discharge, whichever comes first.

Data will be monitored as they are submitted to BSC.

In addition, BSC has implemented specific design and clinical mitigations to address observations from prior preclinical and clinical studies. Please refer to the Investigator Brochure for a detailed description of risk mitigations.

17.6. Anticipated Benefits

The Vortex System is intended to support stable subjects undergoing HR-PCI by temporarily decreasing the load on the heart and ensuring adequate organ perfusion. The benefit of mechanical circulatory support devices is that they provide support in the event the subject becomes hemodynamically unstable during a procedure. Society guidelines state that elective insertion of an appropriate hemodynamic support device as an adjunct to PCI may be reasonable in carefully selected high-risk patients¹⁸. The Vortex design provides mechanical circulatory support and a mechanism of action similar to that of the commercially available Impella[®] devices (Abiomed, Inc., Danvers, MA, USA). Both designs use a cannula and impeller to move blood from the left ventricle into the aorta. The Vortex System may provide improved conformation to subject anatomy and a less complex arrangement during the interventional procedure.

Please see the Investigator Brochure for existing clinical data regarding use of mechanical circulatory support devices and additional information on the Vortex design. Prophylactic use of the Vortex System during HR-PCI procedures should improve patient hemodynamics and may improve patient outcomes.

17.7. Risk to Benefit Rationale

Review of the aforementioned clinical benefits versus risks takes into account the known risks/benefits that have been identified in the published literature on other mechanical circulatory support devices. Risks associated with the investigational device have been estimated, risk controls have been implemented, and an evaluation of residual risk (individual risks and overall risk) has been performed. When used according to the IFU, investigator training, and proctoring, all risks have been reduced as low as possible, and the medical benefits of the investigational device have been determined to outweigh the residual risk.

18. Safety Reporting

18.1. Reportable Events by Investigational Center to Boston Scientific

It is the responsibility of the investigator to assess and report to BSC any event which occurs in any of following categories from time of enrollment through end of study (see definitions in **Table 18.2-1**).

- All serious adverse events (SAE)
- All adverse events (AE)
- All serious adverse device effects (SADE)
- All adverse device effects (ADE)
- All investigational device deficiencies
- All unanticipated serious adverse device effects (USADE)

- All IMR events
- New findings/updates in relation to already reported events

When possible, the medical diagnosis should be reported as the Event Term instead of individual symptoms.

If it is unclear whether or not an event fits one of the above categories, or if the event cannot be isolated from the device or procedure, it should be submitted as an adverse event and/or device deficiency.

Any reportable AE required by the protocol and experienced by the study subject after informed consent and once considered enrolled in the study (see Section 9.1), whether during or subsequent to the study procedure, must be recorded in the eCRF.

Underlying diseases and chronic conditions are not reported as AEs unless there is an increase in severity or frequency during the course of the investigation. Death should not be recorded as an AE but should only be reflected as an outcome of one (1) specific SAE (see **Table 18.2-1** for AE definitions).

Refer to Section 16 for the known risks associated with the study device.

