9.1. Point of Enrollment

Subjects who provide written informed consent and are confirmed eligible for the study are considered enrolled in the study as soon as an attempt is made to insert any part of the Vortex System into the subject's femoral artery (e.g., Vortex sheath).

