d: 12-lead ECG; baseline ECG should be done within 30 days prior to the index procedure; post-procedure timing is per standard of care for HR-PCI.

e: Laboratory tests at baseline include CBC with platelets, serum creatinine, plasma-free hemoglobin, and cardiac enzymes. Post-procedure, cardiac enzymes (CK or troponin is required, CK-MB or troponin if CK is elevated) must be collected once per standard of care within 6–24 hours; if readings are abnormal, a second collection per standard of care is required. Plasma-free hemoglobin must be collected pre-discharge (≥ 6 hours post procedure). Plasma-free hemoglobin may be collected during the index procedure per the standard of care.

f: Minimum required iliofemoral diameter is > 5.5 mm; any assessment technique to determine diameter and tortuosity is permitted; assessment must be done within 365 days prior to the index procedure.

g: TTE assessment should be done within 180 days prior to the index procedure.

h: Deidentified copies of the imaging assessments should be provided to Boston Scientific.

i: Coronary angiogram should be done within 365 days prior to the index procedure per standard of care for HR-PCI.

j: Information on device deficiencies for the test device will be monitored and reported to Boston Scientific.

k: The adverse event assessment includes AE, SAE, ADE, SADE, USADE, and IMR events, which will be collected from the time of enrollment through 72 hours post-procedure or hospital discharge, whichever comes first, in all subjects. Please refer to Section 18.1 for reportable events, including a list of IMR events, and to **Table 24.2-1** for definitions of these events, which specify data required for IMR adjudication.

Abbreviations: AE=adverse event; ADE=adverse device effect; CBC=complete blood count; CCS=Canadian Cardiovascular Society; CK=creatinine kinase; CK-MB=creatinine kinase myoglobin band; ECG=electrocardiogram; HR-PCI=high risk percutaneous coronary intervention; IMR=independent medical

Table 10.1-1: Data Collection Schedule

Assessment	Baseline	Index Procedure	≤72 Hours / Discharge ^a
------------	----------	-----------------	------------------------------------

reviewer; SADE=serious adverse device effect; SAE=serious adverse event; USADE=unanticipated serious adverse device effect

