10.7.1. Vortex System Procedure

The investigational device will be delivered on a guidewire through a Vortex introducer sheath catheter from the femoral artery access site to the aorta and positioned across the aortic valve. During the transcatheter approach, the subject is under conscious sedation.

Please refer to the Vortex IFU and investigator training materials (see Section 15.4.1) for detailed instructions on procedural steps.

Note 1: All Vortex procedures will be performed with the support/presence of trained BSC personnel.

Note 2: Plasma-free hemoglobin may be collected during the index procedure per the standard of care.

The following information will be collected during the procedure. Additional data to be collected will be outlined in the eCRF.

- Date of procedure
- Time of first vascular puncture (femoral) and vascular closure (skin-to-skin time)
- Vortex System insertion and removal time
- Additional information regarding use of the Vortex System
 - Descriptive information on Vortex System insertion procedure
 - Descriptive information on Vortex System positioning and retrieval
 - Descriptive information on the impact of the Vortex System on cardiac anatomy and physiology
 - Impact of Vortex System usage on HR-PCI procedure success
- ECG changes (per standard of care)
- Adverse event assessment; see Section 18
- Device deficiencies assessment

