10.7.3. Intraprocedural Hemodynamic Measurements

Intraprocedural hemodynamic assessment is primarily based on TTE (or intracardiac echocardiography³³ as per standard of care) and catheter-based pulmonary artery measurements. Cardiac output (CO), pulmonary artery (PA) pressure, pulmonary capillary wedge pressure (PCWP), central venous pressure (CVP), mean arterial pressure (MAP), and right atrial pressure (RAP) should be measured before and after the pump is placed and switched on via the pulmonary artery catheter and also when the pump is switched off and

removed (post-procedure). Left ventricular pressure may be measured via the pigtail catheter.

10.8. *Post-procedure (≤ 72 Hours)/Prior to Hospital Discharge*

Within 72 hours post procedure or before discharge (whichever comes first), the following assessments must be performed.

- 12-lead ECG
- Laboratory tests
 - Cardiac enzymes (CK or troponin required, CK-MB or troponin if CK is elevated) must be collected once per standard of care within 6–24 hours post-procedure; if readings are abnormal, a second collection per standard of care is required.
 - Plasma-free hemoglobin must be collected ≥ 6 hours post procedure (before discharge)
- NYHA classification
- Anticoagulation therapy and other cardiovascular medications
- Adverse event assessment (see Section 18)
- Device deficiencies assessment

10.9. *Study Completion*

All subjects will be evaluated through 72 hours or hospital discharge, whichever comes first. A subject's participation in the study will be considered complete after 72 hours or hospital discharge (whichever comes first).

10.10. *Source Documents*

It is preferable that original source documents, when available, are maintained at the investigative center. In lieu of original source documents, certified copies are required to be maintained. A certified copy is a copy (irrespective of the type of media used) of the original record that has been verified (i.e., by a dated signature or by generation through a validated process) to have the same information, including data that describe the context, content, and structure, as the original. Source documentation includes but is not limited to those items noted in **Table 10.10-1**. Source documentation provided to the Sponsor for assessment/adjudication will be deidentified per local law and regulations.

Table 10.10-1: Source Documentation Requirements

Requirement	Disposition

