3.2 Additional Measurements

Safety events will be collected through 72 hours post-procedure or hospital discharge, whichever comes first, as listed below. Death, stroke, bleeding complications, and major vascular complications are adjudicated by an Independent Medical Reviewer (IMR).

- Stroke/transient ischemic attack (TIA)
- Cardiac tamponade
- Cardiac death

- Myocardial infarction (MI)
- Bleeding complications: Type 3–5 based on the Mechanical Circulatory Support Academic Research Consortium (MCS-ARC) definitions
- Acute kidney injury (AKI; based on the AKIN System Stage 3 [including renal replacement therapy] or Stage 2)
- Major vascular complications
- Any device-related adverse event (adverse device effect [ADE]/serious adverse device effect [SADE])
- Any procedure-related adverse event
- Any adverse event related to management practices
- Any adverse event related to patient specific adherence
- Any unanticipated serious adverse device effect (USADE)

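### Adverse event reporting starts at the first attempt to insert a Vortex part, so an access injury between femoral puncture and that attempt need not be reported

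*Protocol*

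**What the plan says.** - **Enrollment.** Protocol 9.1: consented, eligible subjects are "considered enrolled in the study as soon as an attempt is made to insert any part of the Vortex System" into the femoral artery. The sheath is given as an example of such a part.
- **Reporting window.** Protocol 18.1 asks investigators to report events "from time of enrollment through end of study", and requires eCRF recording of reportable events "experienced by the study subject after informed consent and once considered enrolled in the study". Table 10.1-1, footnote k, repeats the window for AEs, SAEs, device effects and reviewer-adjudicated events, "which will be collected from the time of enrollment through 72 hours post-procedure or hospital discharge".
- **Procedure clock.** Protocol 10.7.1 collects, as procedural data, "Time of first vascular puncture (femoral) and vascular closure (skin-to-skin time").
- **Procedure-related events.** Protocol Table 24.2-1 defines these as events that happen in the course of the index procedure or as its direct result. It does not restrict them to the time after enrollment. SAP 3.2 lists "Any procedure-related adverse event" among the additional measurements.
- **Denominators.** The ITT set is the consented and enrolled subjects (Protocol 11.2.1, SAP 4.1), per-protocol is a subset of it, and these sets are the denominators (SAP 7.4.3).
- **Consent.** Protocol 10.3 places consent before any study-specific test or procedure.

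**The concern.** The reporting window opens later than the procedure does. A percutaneous sheath cannot be attempted until the artery has been punctured, so every subject passes through a short interval in which they are consented and have an arterial puncture but are not yet enrolled. Several of the injuries that count as major vascular complications in Table 24.2-1, such as pseudo-aneurysm, arteriovenous fistula, dissection and perforation, can be caused by a puncture.

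Two things follow if such an injury occurs in that interval. If the subject goes on to a Vortex attempt, the rule does not require the injury to be reported. If the team stops before trying the sheath, the subject never enrolls and is absent from the ITT set and the adverse event data.

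This is a first-human-use study whose objective includes safety, and access site complications are among the listed risks (Table 17.1-1). The sponsor's continuing safety review (Protocol 20.1) works from what centers report, so an event outside the window might not reach it. The omission can only lower the observed event counts.

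**Working it through.** **1. Order of events against the rules**

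| Step | Subject's status | AE reporting required? | In ITT? |
|---|---|---|---|
| Consent (Protocol 10.3) | Consented, not enrolled | No | No |
| Femoral puncture (10.7.1, start of skin-to-skin time) | Consented, not enrolled | No | Not yet |
| Attempt stopped before any Vortex part is tried | Never enrolled | No | No |
| Attempt to insert sheath, successful or not (9.1) | Enrolled | Yes | Yes |
| Pump delivery, support, removal, follow-up | Enrolled | Yes | Yes |

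Rows 2 and 3 are the gap. The Table 24.2-1 definition covers row 2 if the index procedure starts at the puncture. Section 10.7.1 suggests that it does by timing the procedure from there, although no section states a start point. On that reading the definition and the window in 18.1 and footnote k disagree.

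**2. Search for text that closes the gap**

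- Protocol 7.3 reports results on enrolled subjects, and 9.2 accounts for enrolled subjects.
- The investigator's general duty to record adverse events (15.2) applies as the protocol specifies, which leads back to 18.1.
- SAP 5.1 says subject disposition may be analyzed, without mentioning subjects who were consented but not enrolled.
- No separate safety set is defined.

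None of these requires reporting for rows 2 and 3.

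**3. Size**

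The plan has no calculated figure to reproduce: the cap of 10 enrolled is described as arbitrary and there is no hypothesis (Protocol 11.1.1). For scale, assume 10 enrolled, no counted event, and one access injury before the Vortex attempt. Intervals are exact (Clopper-Pearson) 95%.

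| Handling | Rate | 95% interval |
|---|---|---|
| As written, event not reported | 0/10 = 0% | 0 to 30.8% |
| Counted, subject later enrolled | 1/10 = 10.0% | 0.3 to 44.5% |
| Counted, subject never enrolled | 1/(10 + 1) = 1/11 = 9.1% | 0.2 to 41.3% |

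**4. How likely is at least one?**

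The documents give no rate, so the per-subject risk p is an assumption. The chance of at least one event in 10 subjects is 1 − (1 − p)^10:

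- p = 1%: 9.6%
- p = 2%: 18.3%
- p = 5%: 40.1%
- p = 10%: 65.1%

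**The case against.** The strongest reply is that the interval is brief and the main device-specific access risk is already covered. Enrollment is triggered "as soon as an attempt is made to insert any part of the Vortex System", so an attempt is enough: a failed or injurious attempt to pass the 16 Fr sheath is enrolled, reportable and in the ITT set. That stands, and it limits the point to the time between puncture and first attempt.

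For subjects who do enroll, some early injuries would be picked up anyway. An injury may be recognized or worsen after the attempt. Section 18.1 also tells investigators to submit events that they cannot separate from the device or procedure. SAP 7.3 sets a wholly missing onset date to the procedure date, and the SAP has no filter that removes a recorded event because it began before enrollment. An investigator might also treat the puncture as part of the attempt. All of this is possible, but none of it is a requirement, and it does not clearly cover a subject who never enrolls.

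It may also be said that the first femoral puncture could serve the PCI rather than Vortex, since 10.7.1 does not say which. The interval exists either way, because the artery has to be punctured before the sheath is tried.

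Three stronger readings are tempting and are not supported:

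- *Complications of the pulmonary artery catheter are also lost.* Section 10.7.3 says hemodynamic values "should be measured before and after the pump is placed and switched on via the pulmonary artery catheter". That places the baseline reading before the pump, not before the sheath, and does not say whether the catheter is study-specific. Exclusion criterion EC16 uses right-heart values but names no measurement method. The catheter may well go in after enrollment.
- *Technical Success is inflated because access failures drop out.* Failed sheath attempts stay in. The endpoint concerns delivery, operation and removal of the device, so a rate that includes subjects in whom no part was tried answers a different question.
- *An abandoned subject uses one of the ten places,* giving for example 8/9 = 88.9% instead of 8/10 = 80% with one device failure. The cap is on enrolled subjects, so no place is used. At full enrollment the same comparison would be 9/10 = 90% against 9/11 = 81.8%, and the previous objection still applies to it.

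**Conclusion.** The point holds in a limited form. As written, the reporting rule does not require an access injury between femoral puncture and the first Vortex attempt to be reported, and it leaves out altogether a subject in whom the attempt is abandoned at that stage. It is also narrower than the protocol's own definition of a procedure-related event.

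One uncounted event is worth 10.0 percentage points (1/10) or 9.1 (1/11) at full enrollment. No test, threshold or decision rule depends on it, because the analysis is descriptive. How often it would happen cannot be judged from the documents.

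The conclusion rests on two readings: that the index procedure includes the puncture from which it is timed, and that an attempt to insert a Vortex part begins with that part and not with the needle. The text favors both without stating either, which is itself a reason to settle the wording. This is an inexpensive improvement to safety ascertainment, not a flaw in the ITT definition or the primary endpoint.

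**What to change.** - **Protocol 18.1 and Table 10.1-1, footnote k.** Start adverse event reporting at the first vascular puncture of the index procedure, and at informed consent for events related to any study-specific invasive step done before that. This brings the window into line with Table 24.2-1. State when reporting ends for a subject who is never enrolled.
- **SAP 5.1.** Commit to a listing of every consented subject who had vascular access but no attempt to insert a Vortex part, with the reason and any adverse event.
- **No change** to the ITT set, its denominators or Technical Success. An early event in a subject who later enrolls then counts in the ITT tables, and one in a subject who never enrolls appears in the listing.

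The cost is a wording change in both documents, one extra listing and probably a few more reported events. No added procedure or subject is needed.

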18.2. Definitions and Classification

Adverse event definitions are provided in **Table 18.2-1**. Administrative edits were made on the safety definitions from applicable regulations and guidance including (but not limited to) ISO 14155 and EU MDR 2017/745/MDCG 2020-10/1 Guidance on Safety Reporting in Clinical Investigations for clarification purposes.

Table 18.2-1: Safety Definitions

Term	Definition
Adverse Event (AE) Ref: ISO 14155 Ref: MDCG 2020-10/1	Any untoward medical occurrence, unintended disease or injury, or any untoward clinical signs (including an abnormal laboratory finding) in subjects, users or other persons, in the context of a clinical investigation, whether or not related to the investigational medical device and whether anticipated or unanticipated. NOTE 1: This includes events related to the investigational medical device or comparator. NOTE 2: This definition includes events related to the procedures involved. NOTE 3: For users or other persons, this definition is restricted to events related to the investigational medical device. NOTE 4: This definition includes events related to management practices NOTE 5: This definition includes patient related events
Adverse Device Effect (ADE) Ref: ISO 14155 Ref: MDCG 2020-10/1	Adverse event related to the use of an investigational medical device NOTE 1: This includes any adverse event resulting from insufficiencies or inadequacies in the instructions for use, the deployment, the procedural treatment, the installation, the operation, or any malfunction of the investigational medical device.

Table 18.2-1: Safety Definitions

Term	Definition
	
NOTE 2: This definition includes any event resulting from use error or from intentional misuse of the investigational medical device.
 
NOTE 3: This includes "comparator" if the comparator is a medical device.


Serious Adverse Event (SAE) Ref: ISO 14155 Ref: MDCG 2020-10/1
	
Adverse event that led to any of the following:
 
 a) Death, b) Serious deterioration in the health of the subject, users or other persons as defined by either: 
 1) a life-threatening illness or injury, or 2) a permanent impairment of a body structure or a body function, including chronic diseases, or 3) in-patient hospitalization or prolongation of existing hospitalization, or 4) medical or surgical intervention to prevent life-threatening illness or injury or permanent impairment to a body structure or a body function c) Foetal distress, foetal death, or a congenital abnormality or birth defect including physical or mental impairment. 
NOTE 1: Planned hospitalization for a pre-existing condition, or a procedure required by the clinical investigational plan, without a serious deterioration in health, is not considered a serious adverse event.

Serious Adverse Device Effect (SADE) Ref: ISO 14155 Ref: MDCG 2020-10/1
	
Adverse device effect that has resulted in any of the consequences characteristic of a serious adverse event.

Unanticipated Serious Adverse Device Effect (USADE) Ref: ISO 14155 Ref: MDCG 2020-10/1
	
Serious adverse device effect which by its nature, incidence, severity, or outcome has not been identified in the current risk assessment.
 
NOTE 1: Anticipated serious adverse device effect (ASADE) is an effect which by its nature incidence, severity or outcome has been identified in the risk assessment.

Serious Health Threat Ref: ISO 14155
	
Signal from any adverse event or device deficiency that indicates an imminent risk of death or a serious deterioration in the health of subjects, users or other persons, and that requires prompt remedial action for other subjects, users or other persons.
 
NOTE 1: This would include events that are of significant and unexpected nature such that they become alarming as a potential serious health hazard or possibility of multiple deaths occurring at short intervals.


Device Deficiency Ref: ISO 14155 Ref: MDCG 2020-10/1
	
An inadequacy of a medical device related to its identity, quality, durability, reliability, usability, safety or performance.
 
NOTE 1: Device deficiencies include malfunctions, use errors, and inadequacy in the information supplied by the manufacturer including labelling.
 
NOTE 2: This definition includes device deficiencies related to the investigational medical device or the comparator.

The following definitions will be used for defining hospitalization or prolongation of hospitalization for SAE classification purposes:
	

Table 18.2-1: Safety Definitions

Term	Definition
Hospitalizations	
Hospitalization does not include:
 
 • Emergency room visit that does not result in in-patient admission 
NOTE 1: Although an emergency room visit does not itself meet the definition for hospitalization, it may meet other serious criteria (e.g., medical or surgical intervention to prevent permanent impairment or damage)
 
 • Elective and pre-planned treatment/surgery for a pre-existing condition that is documented in the subject’s record at the time of consent/enrollment • Admission for social reasons and/or respite care in the absence of any deterioration in the subject’s general condition (e.g., subject is homeless, caregiver relief) • Pre-planned, protocol-specified admission related to the clinical study (e.g., procedure required by protocol)
Prolongation of Hospitalization	
In-patient admission to the hospital that is prolonged beyond the expected standard duration for the condition under treatment.
 
NOTE 1: New adverse events occurring during the hospitalization are evaluated to determine if they prolonged hospitalization or meet another SAE criterion.

